12.1 Protocol-Mandated Correlative Studies

Radiologic Image and RT Structure Collection:

The submission of a RT planning CT scans with associated contours is mandatory for participation in this trial.

The association of a published radiomic signature with EFS will be determined in this population of HPV-related OPSCC patients treated with reduced ENI volumes. Specifically, the 4-feature radiomic signature of Aerts et al./*Aerts 2014*/ will be derived from each gross tumour volume contour using PyRadiomics or comparable software.

Tumour Tissue Collection:

The submission of a representative block of the diagnostic tumour tissue at the request of the CCTG Central Tumour Bank is mandatory for participation in this trial. One tumour block is requested from a biopsy of the primary oropharyngeal tumour. If no primary cancer blocks are available, one block of metastatic lymph node tissue can be sent instead. Where local centre regulations prohibit submission of blocks of tumour tissue, the approval of the CCTG must be sought prior to registration of the first patient to allow cores (two 2 mm cores of tumour from the block) and a predetermined number of slides of representative tumour tissue to be substituted in response to the Central Tumour Bank request.

Somatic mutations and HPV genotype will be detected within tumour DNA in order to determine their prognostic significance in patients treated with reduced ENI volumes. Genomic DNA will be extracted from tumour blocks and peripheral blood leukocytes (germ line) and will be subjected to high throughput sequencing using published methods [Newman 2014]. Briefly, DNA libraries will be constructed from tumour genomic DNA and germline genomic DNA. Targeted sequencing will be performed in order to detect frequent OPSCC-associated HPV genotypes as well as mutations within TP53 and genetic deletions within FHIT (chromosome 3p14 marker).

Blood and Plasma Collection:

The submission of whole blood and plasma is also mandatory for participation in this trial.

Whole blood will be used as a source of germ line DNA (from peripheral blood leukocytes) for targeted sequencing of the TP53 and FHIT genes and comparison with tumour DNA as described above.

Plasma will be used for detection of circulating tumour-derived HPV DNA (ctDNA) levels in pre-treatment and post-treatment plasma. The levels of ctDNA will be measured and correlated with EFS in order to determine prognostic significance. Cell-free DNA will be extracted from plasma and subjected to droplet digital PCR or high throughput sequencing in order to detect HPV sequences. The number of HPV copies per milliliter plasma will be determined for comparison with EFS and with the other putative prognostic biomarkers.

12.2 Optional Banking of Samples

Banking of Radiologic Images and RT Structures:

Mandatory submission of RT planning CT scans with associated contours has been described above. The subsequent banking of collected data is not mandatory for participation in the study, but the participation of all centres is strongly encouraged. Data will be banked by QARC (www.qarc.org).

Proposals to use the banked data for the purposes of assessing markers involved in predicting treatment response and outcomes may be submitted to the bank. A scientific review process of any proposals to use the data will take place and any proposals approved will have undergone ethics approval.

Banking of Tumour Tissue:

Mandatory submission of tumour tissue has been described above. The subsequent banking of collected diagnostic tissue is not mandatory for participation in the study, but the participation of all centres is strongly encouraged. Blocks and blood will be carefully banked as part of the CCTG tissue/tumour bank at Queen's University in Kingston, Ontario.

After patient consent, collection of paraffin tumour blocks will be preferred, as one of the objectives will be to create tissue micro arrays. These will optimize the amount of tissue available to investigators and permit the preservation of the tumour block submitted. If tumour blocks are unavailable, then two x 2 mm cores of tumour from the block and 30 specimen slides are preferred. If, at any time, the submitting hospital requires the block to be returned for medical or legal concerns, it will be returned by courier on request.

Proposals to use the banked specimens for the purposes of assessing markers involved in predicting treatment response and outcomes may be submitted to the bank. A scientific review process of any proposals to use the tissue will take place and any proposals approved will have undergone ethics approval.

Banking of Blood and Plasma:

Mandatory submission of whole blood and plasma has been described above. The subsequent banking of collected samples is not mandatory for participation in the study, but the participation of all centres is strongly encouraged. Samples will be carefully banked as part of the CCTG tissue/tumour bank at Queen's University in Kingston, Ontario.

Proposals to use the banked specimens for the purposes of assessing markers involved in predicting treatment response and outcomes may be submitted to the bank. A scientific review process of any proposals to use the tissue will take place and any proposals approved will have undergone ethics approval.

13.0 STATISTICAL CONSIDERATIONS

13.1 Objectives and Design

This is a phase II single arm trial.

The primary objective is to evaluate the efficacy of primary definitive RT or CRT utilizing volume-reduced ENI as measured by 2-year EFS in patients with low-risk HPV-related OPSCC.

The secondary objectives are to evaluate overall survival, local control, regional control, local-regional control, out-of-field regional control, distant metastasis free survival, early and late toxicities of treatment, subjective swallowing functions, QOL, resource utilization and lost productivity, and prognostic biomarkers.

The tertiary objectives are to assemble an imaging and biospecimen bank for future research that could improve risk stratification and patient selection for volume-reduced ENI.

13.2 Primary Endpoints and Analysis

The primary endpoint is 2-year EFS.

13.3 Sample Size and Duration of Study

We estimate 2-year EFS to be 91% (H_a) for low-risk HPV-related OPSCC. Assuming that the experimental treatment will be considered as ineffective if the 2-year EFS is $\leq 85\%$ (H_0), with one-sided alpha of 0.1, a sample size of 100 patients will have 80% power to detect a 6% difference of 2-year EFS. With 3 years of accrual and 2 years of follow-up, the total duration of this study will be 5 years. A total of 304.7 person-years of follow-up is needed for the final analysis. The null hypothesis (H_0) will be rejected when the observed survival rate is 88.85% or higher (i.e. if there are 18 or fewer EFS events observed).

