13.5 Interim Analysis

A built in interim futility analysis is planned when 162.9 person-years of follow-up are observed. The alternative hypothesis (H_a) will be rejected at significant level 0.05 when 12 or more EFS events are observed. The interim analysis is expected to occur 38 months after trial activation.

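### The stated 80% power is not the power of the stated 18-event success rule, which is about 86%, or about 83% with the futility stop

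*Protocol*

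**What the plan says.** Protocol 13.3 gives the whole design in one paragraph, and SAP 1.2 repeats it almost word for word.

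- Alternative: "We estimate 2-year EFS to be 91" per cent.
- Null: "the experimental treatment will be considered as ineffective if the 2-year EFS is" 85% or lower.
- Error rate: "with one-sided alpha of 0.1".
- Power: "a sample size of 100 patients will have 80% power to detect a 6% difference of 2-year EFS".
- Information: "A total of 304.7 person-years of follow-up is needed for the final analysis".
- Decision: the null is rejected at an observed rate of 88.85% or higher, explained as "if there are 18 or fewer EFS events observed".

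Protocol 13.5 and SAP 1.5 add a futility look at 162.9 person-years, where the alternative is rejected "when 12 or more EFS events are observed". Neither document names the distribution or test behind these figures, or says whether the 80% allows for the futility stop.

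**The concern.** Alpha, power, person-years and event limit are presented as properties of one design, so they should all follow from one rule. The alpha follows from 18 or fewer events. The power does not: it matches a rule one event stricter.

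Power is the figure a reader uses to interpret a failed trial. At 80%, the chance of missing a true 2-year EFS of 91% is 20%. Under the stated rule it is about 14%, or about 17% with the futility stop. A final report that carries the 80% forward would attach the wrong operating characteristic to the primary test.

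**Working it through.** **Inputs.** From protocol 13.3: 2-year EFS of 85% (null) and 91% (alternative), 304.7 person-years, and success with 18 or fewer events. From protocol 13.5: stop with 12 or more events at 162.9 person-years. The one assumption added is a constant hazard.

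**Hazards.** The hazard is λ = −ln(2-year EFS)/2.
- Null: λ0 = −ln(0.85)/2 = 0.08126 per year
- Alternative: λ1 = −ln(0.91)/2 = 0.04716 per year

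**Event count.** At a fixed total person-time T, the count is taken as Poisson with mean λT.
- Final, 304.7 person-years: 24.76 (null) and 14.37 (alternative)
- Interim, 162.9 person-years: 13.24 (null) and 7.68 (alternative)

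**Reproducing the plan's own figures.**
- P(X ≤ 18 | null) = 0.0999, against the stated alpha of 0.1.
- Solving P(X ≤ 18 | null) = 0.10 for T gives 304.66 person-years, against the stated 304.7.
- exp(−2 × 18/304.7) = 88.86%, or 88.85% at the unrounded 304.66, against the stated 88.85%.

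The model therefore recovers the alpha, the person-years and the threshold, all at a limit of 18.

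**Power.** P(X ≤ 18 | alternative) = 0.861, not 0.80. One event lower, P(X ≤ 17 | alternative) = 0.7999. Solving P(X ≤ 17 | alternative) = 0.80 for T gives 304.68 person-years, which also rounds to 304.7. The stated design point is thus where the 18-event alpha condition and the 17-event power condition meet. That is what one would see if exactly 18 events counted as success for alpha and as failure for power.

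**Futility stop.** Success now also needs 11 or fewer events at 162.9 person-years. With an independent increment over the remaining 304.7 − 162.9 = 141.8 person-years, the probability of success is the sum over k = 0 to 11 of P(X1 = k) × P(X2 ≤ 18 − k).

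| Rule at 304.7 person-years | Alpha, no interim | Power, no interim | Alpha, with stop | Power, with stop |
|---|---|---|---|---|
| 18 or fewer (as stated) | 0.0999 | 0.861 | 0.089 | 0.829 |
| 17 or fewer | 0.066 | 0.800 | 0.062 | 0.780 |

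**Cross-check.** A simulation of 100 patients with uniform accrual over 3 years, analysed at 162.9 and 304.7 person-years, gave power 0.864 without the stop and 0.832 with it. The corresponding alphas were 0.099 and 0.087.

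**Other methods.**
- Poisson approximations to the 18-event rule give power of 85.5% (normal) and 86.2% (square root).
- Exact binomial with 100 patients gives 71.2% power at alpha 0.099 (90 or more event-free), or 81.2% at alpha 0.163 (89 or more).
- A normal test on the log hazard gives 79.8% for 100 patients with 3 + 2 years, but its cut-off at 304.7 person-years is 17.7 events, in effect a 17-event rule.

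None of these gives the 18-event rule both alpha 0.10 and power 80%.

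**The case against.** The best defence is that alpha and power in a sample-size sentence are often targets, and a rule on discrete counts can only meet or exceed them. Read so, the sentence is true: the 18-event rule keeps alpha at or below 0.10 and has at least 80% power, even with the futility stop. The sentence also attaches the 80% to 100 patients rather than to the event limit, and the log-hazard approximation shows that a figure near 80% can arise that way. Finally, with the stop included the gap is only about 3 points, and it lies in the safe direction.

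Much of this stands. The error is conservative, and how the 80% was obtained is not documented, so the one-event slip is an inference. The defence does not make 80% the power of the stated rule, however. The text does not call it a minimum, and a loose minimum would not be expected to match a 17-event rule at 304.68 person-years.

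A reader might go further and infer that the limit itself is in doubt between 17 and 18. The documents do not support that. Both state the limit in two forms that agree: 18 or fewer events, and 88.85%. Seventeen events would give exp(−2 × 17/304.7) = 89.44%, and the stated alpha of 0.1 also fits 18 and not 17. A result of exactly 18 events passes as written, because a power figure plays no part in the decision.

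**Conclusion.** The stated 80% is a wrong figure for the stated rule. The 18-event rule has power of about 86% ignoring the interim (6 points above the stated figure), or about 83% with the futility stop (3 points above). Its alpha is 0.100 or 0.089 respectively.

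This rests on constant hazards, which the documents do not state but which reproduce their other final-analysis figures. The figures with the stop also assume that the trial would end whenever the interim count reached 12. The results depend on person-years, so they are not sensitive to whether 99 or 100 patients contribute.

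It would be wrong to conclude that the trial is underpowered, that alpha is exceeded, or that the limit should drop to 17. Power is understated, alpha is kept, and the limit is clear. This is a reporting error in the primary design statement, and no pass or fail outcome turns on it.

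**What to change.** In SAP 1.2, in protocol 13.3 if it is amended again, and in the final report:

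- Keep the rule of 18 or fewer events and 88.85% unchanged.
- Name the model: exponential EFS, with a Poisson event count at fixed person-years.
- Replace the 80% with the rule's own figures: power about 83% and one-sided alpha 0.089 allowing for the futility stop at 12 or more events at 162.9 person-years (about 86% and 0.100 without it).

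Do not substitute a 17-event limit. It would contradict the 88.85% threshold, and with the futility stop its power is 78.0%.

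The cost is a sentence or two of text. No data, patient or threshold is affected.

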13.4 Safety Monitoring

Adverse events will be monitored on an ongoing basis by the central office and their frequencies reported annually at investigators' meetings.

13.5 Interim Analysis

A built in interim futility analysis is planned when 162.9 person-years of follow-up are observed. The alternative hypothesis (H_a) will be rejected at significant level 0.05 when 12 or more EFS events are observed. The interim analysis is expected to occur 38 months after trial activation.

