1.3 Timeline

The analysis will include data accumulated until May 31, 2024 (estimated timing, specific timing decided until 304.7 person-years of follow-up are observed).

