1.5 Interim analysis

A built-in interim futility analysis was conducted when 162.9 person-years of follow-up are observed. The alternative hypothesis (Ha) will be rejected at significant level 0.05 when 12 or more EFS events are observed. The DSMC reviewed the futility analysis at 2023 spring meeting and recommended the trial to continue.

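### The interim futility boundary of 12 or more EFS events at 162.9 person-years does not have the printed level of 0.05

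*Protocol*

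**What the plan says.** Protocol 13.5 plans one interim futility analysis at 162.9 person-years of follow-up. At that look the alternative hypothesis "will be rejected at significant level 0.05 when 12 or more EFS events are observed". The same section adds: "The interim analysis is expected to occur 38 months after trial activation". SAP 1.5 repeats the person-years, the count and the level, and reports the outcome: "The DSMC reviewed the futility analysis at 2023 spring meeting and recommended the trial to continue".

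The hypotheses are in Protocol 13.3 and SAP 1.2. The alternative is a 2-year EFS of 91% ("We estimate 2-year EFS to be 91% (H_a) for low-risk HPV-related OPSCC") and the null is 85% or lower. The final test has one-sided alpha 0.1 and takes place at 304.7 person-years. It rejects the null at an observed rate of 88.85% or higher, that is, "if there are 18 or fewer EFS events observed". SAP 1.3 ties the final data cut to the same person-years ("specific timing decided until 304.7 person-years of follow-up are observed"). On the calendar, Protocol 13.3 says: "With 3 years of accrual and 2 years of follow-up, the total duration of this study will be 5 years".

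Neither document names the test or model behind the interim level, and neither gives the number of EFS events seen at the look.

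**The concern.** The interim level is the chance that a regimen which truly achieves 91% 2-year EFS crosses the futility boundary. It is the error rate of the trial's only formal stopping rule. At 162.9 person-years the alternative predicts fewer than 8 events, and a boundary of 12 is not far enough into the upper tail to carry 0.05. As printed, the rule would reject a regimen on target nearly twice as often as stated.

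The mismatch also leaves one outcome undetermined. At exactly 12 events the printed count says to reject the alternative, while the printed level says not to. With 11 or fewer events, or 13 or more, the two agree. The SAP is the guide for the study report, so the unmatched pair would carry over into it.

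**Working it through.** **Inputs.** 2-year EFS of 91% (Ha) and 85% (H0), 304.7 person-years and 18 or fewer events at the final, from Protocol 13.3. 162.9 person-years, 12 or more events, level 0.05 and month 38, from Protocol 13.5.

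**Model.** With a constant hazard, the events in a fixed number of person-years are Poisson with mean hazard × person-years.
- Ha: −ln(0.91)/2 = 0.047155 per year
- H0: −ln(0.85)/2 = 0.081259 per year

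**Check on the plan's final rule.**
- Mean under H0: 304.7 × 0.081259 = 24.76. P(18 or fewer) = 0.0999, against the printed 0.1.
- Observed rate at 18 events: exp(−2 × 18/304.7) = 88.86%, against the printed 88.85%.
- Power: P(18 or fewer | Ha) = 0.861, against the printed 80%. P(17 or fewer | Ha) = 0.7999.

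The model returns the alpha and, closely, the cut-off, but not the power at 18. It is therefore a good candidate for the design method but is not proved to be it, and other methods are tried below.

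**Interim rule.** Mean under Ha: 162.9 × 0.047155 = 7.68. Mean under H0: 162.9 × 0.081259 = 13.24.

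| Events | Exact P under Ha | Exact P under H0 |
|---|---|---|
| 12 or more | 0.0903 | 0.6705 |
| 13 or more | 0.0497 | 0.5627 |
| exactly 12 | 0.0406 | 0.1077 |

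Confidence limits agree. The exact one-sided 95% upper bound for 2-year EFS is 91.85% with 12 events, which includes 91%, and 90.99% with 13, which excludes it.

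**Other methods, level at 12 events under Ha.**

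| Method | Level at 12 | Critical count for 0.05 |
|---|---|---|
| Score | 0.060 | 7.68 + 1.645 × √7.68 = 12.24 |
| Log rate | 0.061 | 12.28 |
| Mid-P | 0.070 | 13 |
| Square root | 0.083 | 12.92 |
| Score, continuity-corrected | 0.084 | 13 |
| Exact Poisson | 0.090 | 13 |

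A binomial test with 81 patients (about 162.9/2) gives 0.058. Likelihood-ratio, cube-root and Wald versions give 0.075 or more. None reaches 0.05 at 12 events.

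**A possible origin.** The score critical value at the final is 24.76 − 1.2816 × √24.76 = 18.38. Dropping the decimals gives 18, which is correct for a rule of the form *18 or fewer*. Dropping the decimals of 12.24 gives 12, but a rule of the form *or more* has to round up to 13. This is a conjecture.

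**Person-years and timing.** Exact level 0.05 falls at 163.07 person-years for 13 or more events and at 146.8 for 12 or more. Assume 100 patients, uniform accrual over 36 months and no dropout. Then 162.9 person-years falls at 38.6 months under Ha and 39.3 under H0, and 146.8 falls at 36.5 and 37.1. At month 38 exactly, Ha gives 158.7 person-years, where 12 or more has level 0.078 and 13 or more has 0.042.

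**Effect on the whole design.** The chance of a positive trial is the sum over k below the stopping count of P(N1 = k) × P(N2 ≤ 18 − k), where N1 is the interim count and N2 the later events. With the final at 304.7 person-years and 18 or fewer events:

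| Stop | Power | One-sided alpha |
|---|---|---|
| Binding at 12 | 0.829 | 0.089 |
| Binding at 13 | 0.849 | 0.095 |
| None or non-binding | 0.861 | 0.0999 |

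If the final came instead at the planned 5 years under Ha (321.1 person-years, same accrual assumption), power would be 0.785, 0.801 and 0.809.

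**The case against.** The strongest reply is that the operative rule is clear. Both documents print 12 or more and neither prints 13, so only the level attached to that count is wrong. That may be so, but the level is then a misstated error rate and still needs correction.

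A second reply is that the design method is unknown. The Poisson model misses the printed 80% power at 18 events, so 0.09 is one model's answer. This stands in part: 0.09 should be given with its model, and 0.06 by the score test beside it. The mismatch does not depend on the model, because every method tried exceeds 0.05 at 12 events.

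Third, the slip could lie in the person-years. On H0 timing, 146.8 person-years falls at 37.1 months, slightly nearer to month 38 than the 39.3 months for 162.9. Timing therefore does not settle where the slip arose. But SAP 1.5 says that the look was conducted at 162.9 person-years, and at that figure the pair fails.

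Fourth, little changes in practice, and this stands. At 304.7 person-years even a binding stop at 12 keeps power above 80% and alpha below 0.10. The 5-year power figures apply only if the final were run by calendar, which SAP 1.3 does not plan. A missing interim count would also prevent a check of the DSMC decision even if the level were right.

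**Conclusion.** The concern holds. At 162.9 person-years, 12 or more events has a level of 0.090 under Ha by exact Poisson, or 0.060 by the score approximation, against the printed 0.05. The count that meets 0.05 is 13 or more (0.0497 exact). The size of the level rests on a constant hazard and on the method chosen; the direction does not change across the methods tried. The documents do not show which figure is wrong.

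The consequence is limited. The two readings differ only at exactly 12 events, which has probability 0.041 under Ha and 0.108 under H0. The choice of boundary moves power by 0.849 − 0.829 = 0.02. The look is complete, the trial continued, and the final test does not depend on the interim level. The correction should still be made before the study report repeats the pair.

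**What to change.** Check the DSMC record. Then, in SAP 1.5 and the study report, with an annotation to Protocol 13.5, state the method and the boundary actually applied and make the two figures agree:
- If 12 or more was applied, keep the count and replace 0.05 with the attained level: about 0.09 under Ha (exact Poisson, constant hazard), or 0.06 by the score approximation.
- If more than 12 was applied, change the count to 13 or more and keep 0.05.

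In either case report the actual person-years and EFS events at the look. If operating characteristics are given, state their conditions: whether the stop was binding, the final at 304.7 person-years, and 18 or fewer events. For a binding stop at 12 these are power of about 0.83 and one-sided alpha of about 0.089.

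The cost is one or two sentences in the SAP and report and the protocol annotation. Data collection and the final test do not change.

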5.0 PATIENT EVALUATION FLOWSHEET: PRE-TREATMENT, ON STUDY, AND AFTER TREATMENT

All patients entered on study must be evaluated according to the schedule outlined below with documentation submitted according to the schedule in Appendix III.

Required Investigations	Pre-study	During Protocol Therapy (start of treatment until the end of RT)	After Protocol Therapy until Recurrence/Progression	Post Recurrence or Local, Regional or Distant Progression ¹	
History and Physical Exam					
Including: height ² , weight, BSA, tobacco use, performance status, mucosal clinical assessment	≤ 28 days	Weekly	1, 3, 6, 9, 12, 15, 18, 21, 24, 28, 32, 36 months post RT then q6 months until 60 months post RT	q6 monthly from the date of first failure ³	
Direct or indirect visualization of tumour and surrounding area per local standards	≤ 8 weeks		3, 6, 9, 12, 15, 18, 21, 24, 28, 32, 36 months post RT then q6 months until 60 months post RT	At discretion of the investigator	
Laboratory Procedures/Assessments					
CBC with differential, creatinine, bilirubin, AST, ALT, ALP, LDH, albumin, total protein, glucose, magnesium, calcium, sodium, potassium, chloride, PTT, PT/INR			As clinically indicated		
TSH (Free T4 will be measured if TSH is abnormal)	≤ 14 days	As clinically indicated	12 and 24 months post RT	As clinically indicated	
Radiology					
CT or MRI of head and neck (MRI is recommended for base-of-tongue primary tumours)	≤ 8 weeks	Full staging required if failure documented during treatment	At 3 and 6 months post RT, and as clinically indicated	At the discretion of the investigator	
Chest CT or chest X-ray	As clinically indicated		As clinically indicated		
PET-CT scan	≤ 8 weeks		At the discretion of the investigator		
Adverse Events					
Adverse event assessment ⁴	≤ 14 days	Weekly	1, 3, 6, 9, 12, 15, 18, 21, 24, 28, 32, 36 months post RT then q6 months until 60 months post RT ⁵	As clinically indicated	
PRO-CTCAE selected items	≤ 14 days	Last week of RT	3, 6, 12, 24, and 36 months post RT		
Other Investigations					
Pregnancy Test ⁶	≤ 14 days				
Audiogram ¹¹	≤ 8 weeks		6 months post RT		
Tumour HPV status by IHC, PCR, or ISH ⁷	For all patients				
Biopsy ⁸		Recommended for confirmation of first recurrence, first distant metastases or first local/regional progression.			
Phone contact follow-up ⁹			Annually after 60 months post RT		

footnotes on next page ...

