7.0 TREATMENT PLAN

Although the Canadian Cancer Trials Group acts as the coordinating agency for the trial, the responsibility for treatment of patients rests with the individual investigator.

In accordance with CCTG policy, protocol treatment is to begin within 3 weeks of patient registration.

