7.2.18 Central Review of Regional Failures

With reduction of the elective nodal irradiation volumes, there may be increased risk of out-of-field regional recurrence. Rigorous analysis of patterns of failure in the neck will be important for informing the results of this study and any future studies that utilize a similar treatment approach.

Any subject with regional recurrence in the lymph nodes of the neck (either as first or subsequent recurrence) will require central review of the radiological images (CT, MRI, and/or PET-CT) obtained at the time of recurrence in order to categorize the regional recurrence as in-field or out-of-field. The radiological images showing regional recurrence will be submitted within 4 weeks of confirming the recurrence.

The recurrent tumour volume will be identified on the earliest available diagnostic scan that shows the recurrent node. If the identified recurrent lymph node corresponds to a lymph node that was present on the planning scan, the node from the planning scan will be contoured and named “RECUR_NODE.” Otherwise, the identified recurrent lymph node volume will be contoured on the radiological images obtained at the time of recurrence and named “RECUR_NODE”; following registration to the planning scan, the RECUR_NODE volume will be transferred to the planning CT structure set.

The radiation dose received by the RECUR_NODE volume will be determined.

An “in-field regional recurrence” will be defined in cases in which $\geq 95\%$ of RECUR_NODE was within the 95% isodose of PTV_5600.

An “out-of-field regional recurrence” will be defined in cases in which $< 95\%$ of RECUR_NODE was within the 95% isodose of PTV_5600.

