7.3.2 Surgical Treatment Plan for Patients With New Abnormal Lymph Nodes

New lymph nodes that are abnormal based on the clinical and radiographic examinations at 12 weeks post radiotherapy or on any subsequent examinations should be biopsied without delay to confirm regional recurrence.

For a negative biopsy, at the discretion of the treating team, the subject may undergo re-attempt at biopsy, repeat imaging within 1-2 months, or proceed directly to prompt neck dissection.

For a positive biopsy, full re-staging examinations must be performed (Section 5.0). For isolated biopsy-proven regional recurrence, prompt neck dissection is recommended, provided that the disease is deemed to be operable by the treating surgeon. For inoperable isolated regional recurrence, salvage re-irradiation with or without concurrent chemotherapy may be employed at the discretion of the treating team. If there is overlap of the re-irradiation treatment field with the original treatment field, twice daily hyperfractionated radiotherapy should be performed in order to minimize potential late toxicity.

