15.4 Discontinuation of the Trial

If this trial is discontinued for any reason by the CCTG all centres will be notified in writing of the discontinuance and the reason(s) why. If the reason(s) for discontinuance involve any potential risks to the health of patients participating on the trial or other persons, the CCTG will provide this information to centres as well.

If this trial is discontinued at any time by the centre (prior to closure of the trial by the CCTG), it is the responsibility of the qualified investigator to notify the CCTG of the discontinuation and the reason(s) why.

Whether the trial is discontinued by the CCTG or locally by the centre, it is the responsibility of the qualified investigator to notify the local Research Ethics Board and all clinical trials subjects of the discontinuance and any potential risks to the subjects or other persons.

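### The interim futility rule (12 or more EFS events at 162.9 person-years) has level 0.09 under Ha, not the stated 0.05; a boundary of 13 would give 0.05

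*Protocol*

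**What the plan says.** Protocol 13.3 and SAP 1.2 set 2-year EFS at 91% under Ha and 85% under H0, with one-sided alpha 0.1, 100 patients and 80% power. The final analysis takes place at 304.7 person-years, and H0 is rejected with 18 or fewer EFS events.

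Protocol 13.5 and SAP 1.5 add one futility analysis at 162.9 person-years. Both attach level 0.05 to rejecting Ha when the EFS count is 12 or higher. Protocol 13.5 gives the timing: "The interim analysis is expected to occur 38 months after trial activation". Protocol 13.3 gives the calendar: "With 3 years of accrual and 2 years of follow-up, the total duration of this study will be 5 years". SAP 1.5 reports that the look was done, that the DSMC reviewed it in spring 2023, and that it recommended continuing. Neither document gives the number of events seen at the look.

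**The concern.** A futility rule of this kind has one stated error rate: the chance of giving up when the treatment is as good as hoped. A reader, a DSMC member or a team reusing the design would take that chance to be 5%. If the count and the level do not belong together, one of them is wrong, and the documents do not show which was intended.

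The timing also deserves a check. Section 7.2.18 says: "With reduction of the elective nodal irradiation volumes, there may be increased risk of out-of-field regional recurrence". Such recurrences are EFS events, so it is fair to ask whether the only efficacy look could act while patients were still being registered.

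**Working it through.** **Inputs.** S = 0.91 (Ha) and 0.85 (H0), 100 patients, 36 months of accrual and 304.7 person-years with 18 events come from Protocol 13.3. The 162.9 person-years and the count of 12 come from Protocol 13.5. Constant hazard and uniform accrual are assumptions; step 1 shows that they fit the plan.

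**Model.** Yearly hazard λ = −ln(S)/2, giving 0.0472 under Ha and 0.0813 under H0. The event count at a fixed number of person-years is treated as Poisson with mean λ × person-years.

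**Step 1: reproduce the plan's own figures.**
- Final rule: mean under H0 = 0.08126 × 304.7 = 24.76, and P(18 or fewer) = 0.0999, against the stated alpha of 0.1.
- Final survival threshold: exp(−2 × 18/304.7) = 88.86%, against 88.85% stated.
- Final timing: expected person-years at month 60 under H0 are 302.3, against 304.7 stated.
- Interim timing: 162.9 person-years is reached at month 38.6 (Ha) or 39.3 (H0), against month 38 stated.

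The model reproduces the final rule almost exactly and the timing closely, so it is reasonable to apply it to the interim rule.

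**Step 2: the level of the interim rule.** Mean under Ha = 0.04716 × 162.9 = 7.68.
- P(12 or more) = 0.0903
- P(13 or more) = 0.0497
- The difference is P(exactly 12) = 0.0406.

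The stated 0.05 is the probability of more than 12 events, not of 12 or more.

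**Step 3: effect on the whole design.** For boundary c, the chance of passing the look and then finishing with 18 or fewer events is the sum over k from 0 to c − 1 of P(X₁ = k) × P(X₂ ≤ 18 − k). X₁ has mean λ × 162.9. X₂ has mean λ × (304.7 − 162.9) = λ × 141.8, which is 6.69 under Ha and 11.52 under H0. The look is treated as binding.

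| Boundary | P(stop), Ha | P(stop), H0 | Power | Type I error |
|---|---|---|---|---|
| 12 or more | 0.090 | 0.670 | 0.829 | 0.089 |
| 13 or more | 0.050 | 0.563 | 0.849 | 0.095 |

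Without the look, power is 0.861 and type I error is 0.0999.

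**Step 4: timing against accrual (note only).** With no events at all, 100 × (t − 1.5) = 162.9 gives t = 3.129 years, or month 37.5. Events push the look later. Accrual would have to run to about 41 months (Ha) or 43 months (H0) before the look met its end.

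Suppose registration had instead stopped two months after the 12th event. Under constant hazard, simulation gives a mean of 2.6 registrations spared out of 100 at 85% EFS, or 1.5 with a count of 13. Four other hazard shapes with the same 2-year EFS extend these to 1.4–4.7 and 0.7–2.9. Under Ha the figure is 0.2 or less. The lag is an assumption. It allows for the four weeks given for relapse reports in Appendix III and for the option in 7.3.2, after a negative biopsy, of "repeat imaging within 1-2 months".

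**The case against.** The documents do not name the interim test, so 0.05 might come from an approximation. This does not rescue it. A normal approximation gives z = (12 − 7.68)/√7.68 = 1.56, or 0.060. With a continuity correction it gives z = (11.5 − 7.68)/√7.68 = 1.38, or 0.084. Both exceed 0.05.

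A better objection is that little depends on the error. The final rule is unaffected, power stays above 80%, type I error stays below 0.1, and the look is past. All of that stands. It makes this a correction to the reported properties of the rule and leaves the trial's conclusions alone.

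Two stronger readings are tempting, and the documents support neither.

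The first is that the wrong level affected the DSMC's advice. The two boundaries disagree only at exactly 12 events, and the observed count is not given. Nothing can be inferred from the recommendation to continue.

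The second is that the look is defective because it comes too late to limit registration. The timing is as described, but neither document says the look was meant to control enrolment. It can still end the trial about 21 months early, with probability 0.67 under H0. There is other oversight: "Adverse events will be monitored on an ongoing basis by the central office", and section 15.4 begins: "If this trial is discontinued for any reason by the CCTG all centres will be notified in writing". Neither text mentions the EFS count, but no DSMC charter is among the documents, so what the committee saw before the look is unknown. A registration hold would spare few patients at the 85% null, and none if the committee lifted it. It would also signal a high event count to investigators who determine progression in an open-label trial. The gain grows only if true EFS is well below 85% (8.9 spared at 80%, constant hazard, 2-month lag), which is outside the planning values.

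**Conclusion.** The count and the level in Protocol 13.5 and SAP 1.5 do not match. Under Ha, 12 or more events at 162.9 person-years has probability 0.090, and 13 or more has probability 0.0497. This rests on constant hazard and a Poisson count, the model that reproduces the plan's final rule. The error is confined to the interim rule and does not undermine the planned power or alpha. The placement of the look after planned accrual is a design choice worth knowing about, and it needs no correction.

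**What to change.** For this trial, leave the rule as applied and restate its level as 0.09 in SAP 1.5 and the study report. Give the event count at the look alongside it. That costs a sentence in each document.

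For any reuse of the design, choose one of two consistent rules: 13 or more events (that is, more than 12) with level 0.05, or 12 or more with level 0.09. The boundary of 13 gains 0.020 in power (0.849 − 0.829). In exchange, the chance of stopping an ineffective treatment at the look falls from 0.67 to 0.56, and type I error rises from 0.089 to 0.095, still within 0.1. The final rule needs no change under either choice. A registration hold is a matter of preference and is not part of this correction.
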